#### Background

Prospective epidemiological studies consistently showed that high serum levels of testosterone predict the subsequent occurrence of BC, both before and after menopause. After menopause also high oestrogen and low sex hormone-binding globulin (SHBG) levels are associated with increased BC risk, but the association with testosterone persists upon adjustment for estrogens. Also high serum levels of insulin and insulin-like growth factor-I (IGF-I) are associated with increased BC risk. Insulin has gonadotropic properties and stimulates the synthesis of androgens in the ovary; moreover, it inhibits the liver synthesis of SHBG and of two IGF-binding proteins (IGFBP1 and 2), thus increasing the bio-availability of both sex hormones and IGF-I.

In BC patients, overweight and high serum levels of insulin and testosterone are associated with a significantly increased risk of recurrences. We also showed an increased recurrence rate in patients with metabolic syndrome, defined as the presence of three or more of the following: abdominal obesity, hypertension, hyperglycemia, high triglycerides or low HDL cholesterol values.

Our previous DIANA randomized trials showed that an insulin lowering diet, based on traditional Mediterranean ad macrobiotic recipes, significantly decreases body weight, serum testosterone, insulin, and the bioavailability of estrogens and IGF-I, in both healthy women and BC patients. A significant decrease in insulin resistance and serum testosterone also occurred in a randomized trial of moderate physical activity. Consistently, several observational studies suggested that physical activity and weight reduction help preventing both BC and BC recurrences. The WINS randomized trial of low versus high total fat consumption in BC patients showed a significant 24% reduction of recurrences over 5 years.

We now propose a randomized dietary and physical activity intervention trial to reduce BC recurrences (local, distant, or second BC) in BC patients at high risk because of high serum testosterone (>0.4 ng/ml), or insulin (>50 pmol/L), or the presence of metabolic syndrome. In these patients the estimated 5-year cumulative recurrence rate is 30%. Participants will be recruited through hospitals, patients' associations, and the media. We plan to recruit 1,200 patients and to randomize them in two groups: 600 shall receive standard recommendation for healthy lifestyle without, however, any active support; 600 shall receive a combination of individual and group contacts over the course of one year, including kitchen courses, gym and dance classes, common meals and reinforcing meetings, with emphasis on a comprehensive dietary change including low saturated fat and low refined carbohydrates, and high whole grain cereals and pulses consumption. Compliance will be monitored through weight change and plasma glucose, triglycerides, cholesterol and testosterone.

The main analysis will be by intention to treat. Under the hypothesis of reducing recurrence rate by 25% or 33% the statistical power of the study is 80% or, respectively, 90%, (P<0.05, 5-year follow-up).

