#### **Statistical power**

The survival of BC patients in Italy is dramatically increasing: 5-year relative survival increased from 80.6% for patients diagnosed in the early 1990s (Berrino et al, EUROCARE-3) (45) to 85.6% for patients diagnosed in the early 2000s (EUROCARE-4, unpublished). For these patients the estimated relapse free survival is 81.9 (EUROCARE high resolution study, unpublished). Such a survival improvement is accompanied by a postponement of the incidence of relapse (table 4). *Table 4. incidence rate of local + distant recurrences (EUROCARE, unpublished)* 

Follow-up year	relapse rate %	95% confidence interval
1 st	3.4	2.0 -5.8
$2^{nd}$	4.7	3.0-7.5
3 rd	5.1	3.2-8.1
4 th	4.7	2.9-7.8
5 th	2.1	0.9-4.6
$6^{\text{th}}$ to $8^{\text{th}}$	2.2	1.4-3.0

Based on EUROCARE data we estimate that the 5-year distant recurrences plus second ipsilateral or contralateral BC for patients recruited in the first few years after diagnosis will be about 20%. In the subgroup of patients selected on the basis of high insulin and/or testosterone levels (50% of cases with RR of the order of 3), we estimate that about 30% of patients will develop a recurrence or a second primary BC within 5-year follow-up: 360 cases out of 1200. Considering that the WINS randomized study obtained a 24% reduction of recurrence rate changing a single dietary factor (total fat) (39), and that observational studies suggested that a moderate physical activity may reduce recurrence rate by over 40% (28), we hypothesize that a comprehensive dietary intervention plus physical activity will reduce BC recurrence rate by 33% or more, but we consider also a more prudent estimate of 25% reduction.

The following table gives the number of patients (per arm) that we should recruit in order to have 90% or 80% power to detect a significant difference with  $\alpha < 0.05$ , two sided, or one sided ( $\alpha < 0.10$ ).

Power (1-β)	0.9	0.9	0.8	0.8
α	0.05	0.10	0.05	0.10
33% reduction	412	339	313	251
25% reduction	748	614	566	451

Our aim is to recruit 1,200 high risk patients in order to have 600 patients per arm, which shall guarantee 80% chance of getting a significant difference also with 25% reduction, and allowing for 90% compliance in the intervention group and 10% contamination of the control group.

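### The stated powers of 80% (25% reduction) and 90% (33% reduction) at 600 per arm do not share a basis; with the plan's own non-compliance and contamination, the 80% is about 63–66%

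*Combined protocol and SAP*

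**What the plan says.** The last paragraph of the study summary (the first Background section) gives one pair of power figures for one design: "Under the hypothesis of reducing recurrence rate by 25% or 33% the statistical power of the study is 80% or, respectively, 90" per cent, qualified only by "P<0.05, 5-year follow-up". The same section gives the planning risk: "In these patients the estimated 5-year cumulative recurrence rate is 30" per cent.

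The Statistical power section supplies the detail:
- Expected events are "360 cases out of 1200".
- The hypothesis is that the intervention "will reduce BC recurrence rate by 33% or more, but we consider also a more prudent estimate of 25% reduction".
- The table of patients per arm has columns for 90% power at α 0.05 and 0.10, then 80% power at α 0.05 and 0.10, introduced as "two sided, or one sided". One row reads "33% reduction 412 339 313 251". The 25% row gives 748, 614, 566 and 451.
- The conclusion is "Our aim is to recruit 1,200 high risk patients in order to have 600 patients per arm". The rest of that sentence says this number guarantees 80% power at a 25% reduction and also allows for 90% compliance in the intervention group and 10% contamination of the control group.

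Neither section says how the 90% was obtained, or how compliance and contamination entered the calculation.

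**The concern.** Two powers quoted together for one study should come from one sample size, one control risk, one test and one view of adherence. The table suggests that these do not. At two-sided 0.05 it asks for 566 per arm for 80% power at a 25% reduction, so 600 leaves only 34 patients per arm (6%) to absorb both non-compliance and contamination. It asks for 412 per arm for 90% power at a 33% reduction, so there 600 leaves a large margin.

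The reading of a null result is at stake. The main analysis is by intention to treat, so imperfect adherence reduces the contrast being tested. If power for a 25% reduction is about 63–66%, a true effect of that size would be missed about one time in three, not the one in five that the protocol implies. A 25% reduction is the plan's cautious scenario, the one for which readers most need a correct figure.

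**Working it through.** **Inputs.** Control 5-year risk p1 = 0.30 (Background; Statistical power). Intervention risk p2 = 0.225 for a 25% reduction and 0.20 for 33% (the table matches a reduction of one third). N = 600 per arm. Two-sided α = 0.05. Compliance 90%, contamination 10% (Statistical power). Below, d is the difference in risk and p̄ the mean of the two risks.

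**Step 1: reproduce the plan's table.** Continuity-corrected comparison of two proportions:

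m = [z(α/2)·√(2p̄(1−p̄)) + z(β)·√(p1(1−p1) + p2(1−p2))]² / d²

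n = (m/4)·[1 + √(1 + 4/(m·d))]²

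- 0.30 v 0.20, 90% power: m = 391.9, n = 411.7, rounded up to 412.
- 0.30 v 0.225, 80% power: m = 539.1, n = 565.4, rounded up to 566.

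The other six cells (339, 313, 251, 748, 614, 451) also reproduce exactly. The table therefore compares 5-year proportions and contains no dilution.

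**Step 2: power at 600 per arm, full compliance.**

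Power = Φ{[d − 1/N − 1.96·√(2p̄(1−p̄)/N)] / √([p1(1−p1) + p2(1−p2)]/N)}

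- 25%: (0.075 − 0.00167 − 0.04979)/0.02531 = 0.930, so 82.4%.
- 33%: (0.100 − 0.00167 − 0.04900)/0.02483 = 1.987, so 97.7%.

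**Step 3: power at 600 per arm with the plan's dilution.** The documents give no formula. Assume that it is linear on 5-year risk: intervention arm 0.9·p2 + 0.1·p1, control arm 0.9·p1 + 0.1·p2. The difference shrinks to 0.8·d.

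- 25%: 0.2925 v 0.2325. (0.060 − 0.00167 − 0.04979)/0.02534 = 0.337, so 63.2%.
- 33%: 0.29 v 0.21. (0.080 − 0.00167 − 0.04900)/0.02489 = 1.178, so 88.1%.

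Dropping the 1/N term gives the uncorrected values.

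| Basis, 600 per arm, two-sided 0.05 | 25% reduction | 33% reduction |
|---|---|---|
| Printed | 80% | 90% |
| Full compliance, corrected (uncorrected) | 82.4% (84.0%) | 97.7% (98.0%) |
| 90% compliance and 10% contamination, corrected (uncorrected) | 63.2% (65.6%) | 88.1% (89.4%) |

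On the diluted basis the 80% is too high by 80 − 65.6 = 14.4 to 80 − 63.2 = 16.8 points.

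**Step 4: size needed for 80% at a diluted 25% reduction.** The Step 1 formula with 0.2925 v 0.2325 gives 843 per arm uncorrected and 876 corrected. As a rough check, keeping 80% of the difference inflates n by about 1/0.8² = 1.56, whereas 600/566 is only 1.06.

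**Step 5: other bases.** Figures are uncorrected and for a 25% reduction unless stated.

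- Non-compliance alone: 75.4%. Contamination alone: 76.2%.
- One-sided 0.05 with both: 76% (94% for 33%).
- About 80% returns only if 95% of the difference survives (80.2%), half a 10% loss from a single source.
- Reductions read as hazard ratios 0.75 and 0.67 at full compliance (Schoenfeld): 73% and 94%.
- For control risks from 10% to 50%, any n giving 80% at a 25% reduction gives about 96–97% at 33%.

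None of these yields 80% and 90% together as point values.

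**The case against.** The best defence reads the printed pair as lower bounds from the table. It tabulates only two power levels. At two-sided 0.05, 600 exceeds 566 but not 748 for a 25% reduction, and exceeds 412 for 33%. The highest tabulated levels met are therefore 80% and 90%, exactly the printed pair. This stands at full compliance, and the summary would then lack only the words *at least*. It does not rescue the Statistical power section, which claims the 80% with non-compliance and contamination allowed for; on that basis 80% is not a lower bound.

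A second defence is that the 25% is already the net intention-to-treat effect. Then about 82% applies, but nothing is left for a further allowance, and the protocol presents the allowance as additional.

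Third, linear dilution is this review's assumption. That is fair, and the exact shortfall depends on it. But either source of dilution alone already takes power below 80%.

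A reader might go further and infer that the 90% was taken from the 412-per-arm cell, so that power for a 33% reduction is understated by about 8 points (97.7 − 90). The documents do not support this. They give no derivation of the 90%, it is nearly recovered at 600 per arm with the stated dilution, and the 98% needs full compliance, which the plan does not assume. Nor does the finding show that the trial must be enlarged: power for the main hypothesis of 33% or more remains about 88%.

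**Conclusion.** Wrong as written. The 80% and 90% are not the powers of one study on one basis. On the basis that the Statistical power section says the design allows for, the 90% for a 33% reduction is about right (88–89%), and the 80% for a 25% reduction is overstated by about 14 to 17 points (63–66%). At full compliance both printed figures hold, but only as lower bounds (about 82% and 98%).

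These results rest on a 30% control risk, 600 per arm with no loss to follow-up (the documents give no rate), two-sided 0.05, a comparison of 5-year proportions as in the protocol's table, and linear dilution.

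**What to change.** In the study summary and the Statistical power section, give the same pair at 600 per arm on the plan's diluted basis: about 63% for a 25% reduction and about 88% for 33%. State the control risk, test, continuity correction and dilution formula. If the full-compliance pair (about 82% and 98%) is also shown, label it as such. Remove the statement that 600 per arm guarantees 80% at a 25% reduction while allowing for 90% compliance and 10% contamination.

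The cost is one sentence in each section and one recalculation. Enrolment, follow-up and analysis do not change. The downside is a less favourable stated power for the 25% case.

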#### Background

There is increasing scientific evidence that endogenous hormones and metabolic factors effect breast cancer incidence and prognosis (Figure 1).

*Figure 1. Hormonal, metabolic and dietary correlates of breast cancer risk and recurrences* 

Figure 1 Hormonal, metabolic and dietary correlates of breast cancer risk and recurrences

#### Serum testosterone levels effect BC risk

Prospective epidemiological studies consistently showed that high serum levels of testosterone predict the subsequent occurrence of BC, both before (1-3) and after menopause (4-6). The relative risk (RR) increases linearly with increasing testosterone levels, and the women in the top quartile or quintile of testosterone distribution are 2 to 4 times as likely to develop BC compared with women in the bottom quantile. After menopause also, high estrogen and low SHBG levels are associated with increased BC risk. When testosterone and estradiol are included in the same model, however, the effect of testosterone is greater than that of estradiol (4-6). Consistently with the elevation in risk with increasing endogenous testosterone level, menopausal women using estrogens and testosterone as hormonal replacement therapy (HRT) have a significantly increased BC risk compared with estrogen only therapy and greater risk also compared with estrogen and progestogens therapy (7). Moreover, HRT with synthetic testosterone-derived progestogens are associated with a significantly greater BC risk compared with those with natural (micronized) progesterone (8). The mechanism underlying the association between and rogens and BC risk is not well understood. Androgens may act directly, stimulating the growth and division of BC cells via binding to the androgen receptor or the estrogen receptor (9), or indirectly, via conversion to estrogens in target tissues (10), or by increasing the bioavailability of estradiol because of the greater affinity of testosterone and dihydrotestosterone with SHBG.

#### Insulin and related metabolic factors effect BC risk

Overweight and sedentary lifestyle are associated with insulin resistance. Women who gain weight in adulthood and overweight postmenopausal women have a greater risk for BC than lean women (11, 12). Postmenopausal women who engage in regular exercise (> 3 hours per week) have a reduced risk for BC compared with inactive women (13, 14). Several epidemiological studies found that high serum insulin and IGF-I levels are associated with increase BC risk (15-20), with, however, some inconsistencies as for the effect modification of age and menopausal status.

Insulin and testosterone effect prognosis in BC patients

In BC patients, high serum levels of insulin (21) and testosterone (22 and Micheli et al, submitted) are significantly associated with increased risk of recurrences; after adjustment for traditional prognostic factors (cancer stage at diagnosis, ER and PR) the RRs for BMI and for insulin in the upper quartile were about 2, while the RRs for testosterone in the upper tercile ranged from 2 to 7. We also found a borderline significant association of ER+ cancer with serum levels of estradiol, which, however, disappeared upon adjustment for testosterone levels (22). Testosterone levels are higher than estradiol levels, are easier to measure reproducibly and have lower intra- individual variability (23-25). For this reason, and because it proved to be predictive at any age, we chose testosterone as the main hormonal indicator of BC risk.

We also showed an high risk of recurrence in patients with metabolic syndrome, defined as the presence of three or more of the following factors: abdominal obesity (waist circumference >88 cm), hypertension (SBP>130 and /or DBP >85), hyperglycemia (>110mg/100ml), high triglycerides (>150 mg/100ml) or low HDL cholesterol (<50 mg/100ml) (26) (Table 1). Consistently, several observational studies suggested that sedentary habits (28) and overweight (27) are associated with increased BC incidence and BC recurrences.

Table 1. Hazard ratio of developing recurrences during 5.5-year follow-up of 110 BC patients according to the presence or absence of metabolic syndrome and serum testosterone levels above or under the median value (26).

Metabolic	Testosterone	Recurrence		Hazard	95% C.I
syndrome	>0.40 ng/ml	Yes	No	Ratio	
No	No	7	46	1	
Yes	No	1	3	2.2	0.2-19.4
No	Yes	17	24	3.8	1.5-9.5
Yes	Yes	7	5	6.7	2.3-19.8

# Healthy diet and physical activity decrease insulin and testosterone levels

The DIANA (Dlet and ANdrogens) randomized controlled trials showed that a highly satiating and insulin lowering diet, based on traditional Mediterranean ad macrobiotic recipes, significantly decreases body weight, serum testosterone and the bioavailability of both estrogens and IGF-I, in healthy postmenopausal women (29, 30) and in BC patients (22). In these trials' testosterone decreased by 18% and, respectively, 10% (tables 2 and 3).

A randomized trial of 12-month physical activity versus stretching in healthy postmenopausal women proved that moderate intensity sports/recreational activity can reduce serum insulin (31), testosterone (32), and, to a lesser extent, estrogen levels (33). Among exercisers who lost >2% body fat, testosterone declined by 10% and free testosterone by 12% (P < 0.01 compared with controls). In a randomized trial, Mediterranean-style diet with increased consumption of whole grains, vegetables, fruits, nuts, and olive oil, succeeded in significantly reducing the prevalence of metabolic syndrome and insulin resistance (34).

Table 2. DIANA-1: Hormonal changes after 5 months of insulin lowering diet in healthy postmenopausal women: % change in the intervention group and P value with respect to the change in control group (52 women each) (29,30)

	% change	P		% change	Р
Testosterone	-18	**	Glucose	-6	*
Estradiol	-18	ns	Insulin	-10	ns
Free testosterone	-29	**	Insulin AUC( a )	-8	*
Free estradio1	-23	*	C-peptide	-19	*
SHBG	+25	**	IGF-I	-6	ns
Triglycerides	-1	ns	IGFBP-1	+12	**
Total cholesterol	-14	**	IGFBP-2	+30	**
BMI	-6	**	Waist circumfer.	-5	**
* $P < 0.05$ ** $P < 0.01$ ( a ) area under the curve during a glucose tolerance test					

Table. 3 - DIANA-2: Hormonal changes after 12 months of insulin lowering diet in breast cancer patients (N =110) (22 and unpublished)

	% change	P		% change	Р
Testosterone	-10	*	Glucose	-5	*
Estradiol	-6	*	Insulin	-17	*
SHBG	+5	*	IGF-I	-4	ns
Triglycerides	-14%	*	PDGF	-38	**
Total cholesterol	-11%	*	Systolic BP	-1	*
BMI	-5	**	Waist	-4	**

\* P < 0.05 \*\* P < 0.01 with respect to baseline values

#### **Mechanistic considerations**

Various mechanism by which diet and life-style may promote increased risk for and progression of breast cancer, summarized in figure 2, have been recently reviewed (16, 27, 35). In short, sedentary lifestyle, overweight, hyper-caloric diet, high saturated fat and high glycemic index food are major determinants of metabolic syndrome, which in turn is associated with insulin resistance and increased androgenic activity. Insulin stimulates the synthesis of androgens in the ovary and the expression of GH receptors, and inhibits the liver production of SHBG and IGFBP1 and 2, thus increasing the bio-availability of both sex hormones and IGF-I. IGF-I is increased by a diet rich in protein, in particular milk protein (36). Alcohol intake increases the synthesis of androgens and estrogens (37). Postmenopausal overweight is associated with increased concentrations of total and free androgens, increased peripheral conversion of androgens into estrogens, decreased SHBG, and increased insulin levels. Sedentary lifestyle is associated with higher levels of estrogens, androgens (38) insulin (39) and C-peptide (40).

Figure 2. Mechanistic relationship between diet, physical activity and hormones

#### Previous randomized dietary intervention trials to decrease BC recurrences

Two randomized trials carried out in the eighties on a small number of BC cases (about 100 each) suggested that calorie restriction may reduce BC recurrences (41) and total mortality (42). The Women's Intervention Nutrition Study (WINS), a large randomized controlled trial investigating the role of dietary fat reduction on relapse-free survival in postmenopausal women with early-stage resect able BC (n = 2,700), found that patients on the reduced-fat diet had a lower risk of recurrence (hazard ratio = 0.76, 95% CI = 0.60-0.98) than women on the standard diet (39). A further large-scale trial aimed at reducing fat and increasing fruit and vegetable intake in women diagnosed with BC is currently ongoing (43).

#### Study aims and design

We propose a randomized intervention trial of diet and physical activity to reduce BC relapse (local, distant), and second ipsilateral or contralateral BC, in BC patients at high risk of recurrence because of biochemical markers of increased risk, namely high serum testosterone and/or high fasting insulin and/or metabolic syndrome. Several other markers of increased recurrence risk are available, such as cancer stage at diagnosis, histological grade, hormonal receptors and other gene expression profile. All these will be registered, but we are specifically interested in markers of the host that can be modified through life-style.

### Secondary aims include assessing:

- the effect of the combined dietary and physical activity change on the prevalence of metabolic syndrome and on biomarkers that are hypothesized to be intermediate factors in the association of diet and physical activity with BC

- the effect of the intervention on the development of other life-style related health conditions, such as other cancers, diabetes, hypertension and dyslipidemia, and on total mortality.

#### Phases of the study and milestones:

Identification of eligible patients, Recruitment, Randomization, Intervention, Baseline and yearly measurements, Compliance evaluation, Follow up, Statistical analysis

## Identification of eligible patients

Inclusion criteria:

1) Mastectomy or conservative surgery for invasive breast carcinoma, any type, in the last five years (we expect to recruit mostly patients at the time of diagnosis or at the end of the first follow-up year after surgery, i.e when chemotherapy has been concluded and hormonal therapy, if necessary, started)

2) Absence of signs or symptoms suggestive of recurrences Presence of one or more of the following endocrine/metabolic indicators:

- serum testosterone level ≥ 0.4 ng/ml (1 nmol/ml), corresponding to the median value in BC patients, or
- serum insulin ≥ 7 uU/ml ( 50 pmol/L), corresponding to the upper quartile of insulin distribution in BC patients, or
- metabolic syndrome, present in about 15% of BC patients

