### **Baseline and yearly measurements**

Height and weight: electronic scale with women in light clothes and without shoes. In a sample of cases body fat and lean mass will be measured with bioelectric impedance.

Blood pressure: electronic device.

Serum glucose, triglycerides and cholesterol: standard quality controlled laboratory techniques Serum Testosterone and Insulin: Radioimmunoassay (RIA). For testosterone we shall use a direct RIA kit which has been validated by comparison with indirect assay after organic extraction of serum samples and celite purification (44).

For a sample of patients, we plan to apply for further financial support to measure several other metabolic, endocrine and inflammation markers (estrogens, SHBG, IGF-I, IGFBP 1, 2 and 3, C-reactive protein, leptin and adiponectin) as well as the DNA polymorphism and RNA expression of several relevant gene, in collaboration with the Dept of Oncology of the Ospedale Civico ARNAS in Palermo and at the Institute of Endocrinology at the Milan University.

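### The testosterone entry criterion gives two cut-offs, 0.4 ng/ml and 1 nmol/ml, that are not equivalent; 0.4 ng/ml is evidently intended, and the bracketed figure should be corrected or removed

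*Combined protocol and SAP*

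**What the plan says.** Under Identification of eligible patients, the first endocrine/metabolic indicator reads "serum testosterone level ≥ 0.4 ng/ml (1 nmol/ml"). The criterion equates this cut-off with the median among breast cancer patients, and the insulin and metabolic-syndrome alternatives follow. Any one of the three is enough for entry.

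The same cut-off appears in two other places, in mass units only:

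- The opening Background summary describes the high-risk group by "high serum testosterone (>0.4 ng/ml), or insulin (>50 pmol/L), or the presence of metabolic syndrome".
- Table 1, in the section on insulin and related metabolic factors, splits 110 earlier patients by "serum testosterone levels above or under the median value". Its column head gives that split as above 0.40 ng/ml.

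The molar figure occurs nowhere else. On the assay, Baseline and yearly measurements says "For testosterone we shall use a direct RIA kit which has been validated by comparison with indirect assay". It gives no reporting unit, and no section says which unit decides eligibility.

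**The concern.** This is a figure inside a rule that decides who is randomized. When a threshold is given in two units, a reader may use either, so both must mark the same concentration. Here they do not.

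The plan recruits through three institutes. Under Randomization, women who miss the high-risk criteria are followed as an external low-risk group. If a laboratory reported in nmol/L and the cut-off were read as 1, some women who belong in that outside group could be randomized instead. The intended enrichment for high risk would then be weaker at that site. Table 1 shows why the split matters to the design: recurrence was (17 + 7)/53 = 24/53 = 45% above 0.40 ng/ml, and (7 + 1)/57 = 8/57 = 14% at or below it.

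**Working it through.** **Inputs**

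- Mass cut-off: 0.4 ng/ml (inclusion criteria; also the opening summary and Table 1).
- Bracketed equivalent: 1 nmol/ml (inclusion criteria only).
- Molar mass M of testosterone: not in the documents. Assumption: C19H28O2, so M = 19 × 12.011 + 28 × 1.008 + 2 × 15.999 = 288.43 g/mol. A range of 280 to 300 g/mol is shown to test sensitivity.

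**Step 1. Try to reproduce the bracketed figure.** nmol/ml = (ng/ml) / M = 0.4 / 288.43 = 0.00139 nmol/ml, which is 1.39 nmol/L. The printed 1 nmol/ml is not reproduced.

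**Step 2. Convert the bracket back to mass units under both readings.**

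| Reading of the bracket | In ng/ml (M = 288.43) | Against 0.4 ng/ml | For M = 280 to 300 |
|---|---|---|---|
| 1 nmol/ml, as printed | 288 | 288.43 / 0.4 = 721 times | 700 to 750 times |
| 1 nmol/L, likely intended unit | 0.288 | 0.288 / 0.4 − 1 = −28% | −30% to −25% |

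Over the same range of M, 0.4 ng/ml is 1.43 to 1.33 nmol/L.

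**Step 3. Does the result depend on M?** No. The pair would agree as printed only if M were 0.4 g/mol, and under the nmol/L reading only if M were 400 g/mol.

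**Step 4. Could the bracket be a rounding?** To one significant figure, 1.39 nmol/L does round to 1. But a rounded 1 nmol/L covers 0.5 to 1.5 nmol/L, which is 0.144 to 0.433 ng/ml. That is too coarse for an entry threshold at 0.4 ng/ml, and the unit would still be wrong by a factor of 1,000.

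**Step 5. Compare the neighbouring criterion.** The insulin line, "serum insulin ≥ 7 uU/ml ( 50 pmol/L), corresponding to the upper quartile of insulin distribution in BC patients, or" also gives two units. With assumed factors of 6.0 to 7.175 pmol/L per uU/ml, 7 uU/ml is 42 to 50 pmol/L, so that pair is roughly consistent. The testosterone line is the outlier.

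**Step 6. Does the molar figure enter the design calculations?** No. Statistical power starts from about 20% five-year risk overall, half of patients selected, and a relative risk of about 3. If r is the risk in the unselected half, 0.5r + 0.5 × 3r = 20%, so r = 10% and 3r = 30%. The plan then takes 30% of 1,200 = 360 events. No concentration in molar units is used.

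**Step 7. Inequality sign.** The summary and Table 1 use strictly greater than; the criterion uses greater than or equal to. This affects only a result exactly at the cut-off. The summary and the criterion differ in the same way for insulin.

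**The case against.** The strongest reply is that nobody is likely to be misled. The value 0.4 ng/ml stands in three places and leads the criterion itself. The criterion also ties the cut-off to the median in breast cancer patients, which Table 1 puts at 0.40 ng/ml. Taken literally, the molar figure is so large that it could not be used unnoticed. Harm needs someone to correct the unit to nmol/L, keep the 1, and disregard the mass value beside it. No section says that any site reports in nmol/L, and a single assay method is described. All of this stands, and it limits the expected harm. It does not make the two figures agree, and no section says which governs.

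A reader might go further and infer that the trial would be diluted and fall short of its planned power. The documents do not support that. Such a calculation needs four things they do not supply:

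- **A testosterone distribution.** Only a median is given, with no shape or spread.
- **Misreading everywhere.** The plausible error is at one site or laboratory. Under Feasibility, the smallest centre treats about 200 of some 4,200 patients a year (3,000 + 1,000 + 200), so the effect could be very small.
- **No other route to entry.** Women between 0.288 and 0.4 ng/ml who meet the insulin or metabolic-syndrome criterion are eligible anyway.
- **An average low-group risk just below the median.** The section on testosterone and breast cancer risk describes risk rising linearly with level. If recurrence behaves similarly, women just below the cut-off carry more than the average risk of the lower half.

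Nor do the documents show that eligibility has differed between centres. That is a possibility, not a finding.

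**Conclusion.** The bracketed equivalent in the testosterone criterion is wrong as written, under either reading of its unit. With M about 288 g/mol, it is some 720 times the mass cut-off as printed, and 28% below it if read as nmol/L. The conclusion that the figures disagree does not rest on the exact molar mass.

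The consequence is conditional. Only a site or laboratory that worked in molar units and applied 1 nmol/L would admit extra women: those between 0.288 and 0.4 ng/ml who do not already qualify through insulin or metabolic syndrome. How many they would be, and what they would cost in event rate or power, cannot be computed from the documents. The stated sample size and power are unaffected by the error. Severity is minor: a certain slip in an operative criterion, with the intended value clear from the rest of the plan.

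**What to change.** In the inclusion criteria, either correct the bracket to the true equivalent of 0.4 ng/ml (about 1.39 nmol/L) or delete it, and state that the ng/ml value governs. Naming the reporting unit for the testosterone assay under Baseline and yearly measurements would close the gap completely. Use the same inequality sign in the opening summary and the criterion, for insulin as well as testosterone.

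The cost is a one-line correction to the criterion and a matching edit to the summary, with no change to sample size or analysis. If women have already been enrolled, the sponsor should also confirm which unit each laboratory used when eligibility was decided.
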